An analysis of reinforcement studies from psychosocial/non-methadone clinics (Petry et al, 2004, 2005a, 2006a,2011a,2012a) suggests that longer durations of abstinence during treatment yield greater long-term benefits. Of 1074 patients randomized to a standard care or a standard care plus reinforcement intervention for 12 weeks, 1011 (94.1%) completed a 9-month follow-up and were coded as abstinent throughout 12 weeks of treatment and 9 months of follow-up (via urinalysis and self reports) or not (either index indicating use). Controlling for site, demographics (age, gender, education, race), and baseline drug use, longest duration of abstinence was significantly related to abstinence throughout the 9 month follow-up,  $Beta(SE)=-.18(.02)$ ,  $Wald=91.61$ ,  $p<.001$ , with each additional week of abstinence associated with a 19% increased chance of abstinence post-treatment (95%CI=1.15-1.24). Longer term exposure to reinforcement (24 in the proposed study vs 12 weeks in completed studies), in conjunction with the extended effects noted with VI schedules in general, should further increase durations of abstinence, arguably the best predictor of long-term outcomes.

We have pilot data suggesting that providing reinforcement for longer durations should increase abstinence. A total of 238 alcohol-dependent patients have been randomized to standard care (SC), SC+12 weeks of reinforcement for submitting negative breath samples, or SC+24 weeks of reinforcement for submitting negative breath samples. There is a strong linear association between time receiving reinforcement and longest duration of abstinence, whether abstinence is defined by negative samples alone,  $F(2,235) = 6.75$ ,  $p<.001$ , or with self reports,  $F(2,235)=6.75$ ,  $p<.001$ . On average, patients in SC achieved  $7.8 \pm 6.8$  weeks of abstinence vs  $10.5 \pm 7.4$  and  $12.4 \pm 8.5$  weeks for those assigned to the 12 and 24 week reinforcement conditions, respectively.

[figure not shown]

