During the COVID-19 outbreak and until exposure risks to participants and research assistants are reduced, study visits will be completed over the phone. Participants who complete follow-up visits over the phone will miss some components (i.e. sample submission) but will receive the full \$50 follow-up payment. If the interval between the remote follow-up and opportunity to collect samples/measures is minimal, participants may be able to submit these missed components after risk decreases. Payments for completed mailed packets will remain \$30.

**Incarceration:** This is a minimal risk study that recruits non-prisoner patients from substance abuse treatment programs. However, a portion of the study patients are likely to be incarcerated during the study period due to illegal activities that are common in this population. If a patient is incarcerated during study participation, all study procedures are suspended except the evaluations. In the ICF, patients indicate whether or not they would like the evaluation questionnaires sent to them in prison. The mailing delivered to the incarcerated patient only contains the evaluation questionnaires and a cover letter indicating the questionnaires are follow-up to a study the patient participated in at the University of Connecticut Health Center. A stamped and addressed return envelope is also provided with the questionnaires. If the patient completes and returns the questionnaires for Month 1, 3, 6, 9, 12, 15 or 18, they will receive \$30 in the form of a check. The patient will receive the check after their release from incarceration or they may designate a person to whom the check should be sent during their incarceration. The patient is notified in the ICF that their participation in this study while incarcerated will have no effect on their eligibility for parole.

**Randomization:** Patients will be randomly assigned to one of the three conditions. An urn randomization program (Stout et al., 1994), will balance patients based upon baseline sample results (cocaine positive or negative) and whether or not they were in a controlled environment in the past month (e.g. jail, inpatient detoxification). These variables are used because initial toxicology results are a strong predictor of outcomes (Petry et al., 2004; Preston et al., 1998; Stitzer et al., 2007), and controlled environments impact drug use. A separate 'urn' will be employed in each clinic, thereby stratifying on clinic as well.

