**Data Analysis.** An important issue preceding analyses is to identify baseline differences between groups despite random assignment. Differences between groups that may be related to outcome (e.g., psychiatric diagnoses, dependence severity, clinic services received) will be used as covariates or fixed factors, as appropriate. Analysis will be conducted on an intent-to-treat basis, using all randomized patients, and both short-term (changes from baseline to month 6) and longer-term (throughout the 18-month follow-up) efficacy will be evaluated. The primary outcome is longest duration of cocaine abstinence, a continuous variable that can be transformed if needed. Groups will be compared using t-tests for normally distributed data, or ANCOVA if covariates are included. The design includes 3 treatment groups, allowing for analyses of two main effects.

Primary aim # 1 is to examine the efficacy of adaptive progressive VI reinforcement. We will compare those randomized to Group C vs Group A with respect to longest duration of abstinence during the 24-week intervention period and throughout the 18-month follow-up period.

Primary aim #2 is to assess if adaptive reinforcement improves duration of abstinence achieved relative to traditional reinforcement. We will compare those randomized to the two reinforcement conditions with respect to during treatment and long-term abstinence outcomes.

Secondary aims are to evaluate the impact of the interventions on other indices of stimulant and secondary drug use outcomes. Using the same contrasts above, we will compare groups with respect to: proportions of submitted and expected samples that test negative for stimulants and other drugs (alcohol, opioids, THC), and subjective reports of use (SUC % abstinent days). The first rely on objective indicators and such data will be available from all randomized patients. Subjective reports will supplement objective indices, and patients can be considered using if either index is positive. In terms of proportional data, missing samples will be considered missing (not impacting the denominator) in one analysis, and positive in another to consider the range of possibilities with respect to drug use outcomes. Because Group B has more expected samples (48) than the other groups ( $\geq 18$ ), proportional data for expected samples will rely upon the cell phone prompted samples ( $\geq 18$ ), designed to be similar across conditions, to conservatively test group differences.

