To determine if patient factors predict outcome, multiple regression analyses will be used to find predictors of continuous measures (e.g., longest duration of abstinence, percent negative samples), and logistic regressions for dichotomous dependent variables (e.g., presence or absence of stimulant use at follow-up). Cox regression analyses may also be used to determine what factors predict time to event outcomes, such as time to first positive sample after study initiation. Independent variables will include treatment condition, site, days attended groups at the clinic, drug use severity (ASI-drug scores, baseline positive samples), scores on cognitive control tasks at baseline (computer task or impulsivity scores), and demographics, including gender and race. Analyses will be conducted for the entire sample and with interactions of predictors with condition to assess if certain characteristics are more predictive of outcomes in the different treatment conditions.

Behavioral changes that result from treatment may also be a function of improving cognitive control, and reinforcement interventions may lead to reductions in drug use by enhancing cognitive functioning. If effects of reinforcement on drug use outcomes are significant, cognitive control as assessed via computer and impulsivity tasks will be evaluated as a potential mediator of effects. A latent growth model using structural equation modeling can be built. Models will be built sequentially, starting with a basic latent growth model comprising drug use days over time, modeled as slope and intercept. Important cognitive performance indices can be tested as mediators in turn. A bootstrapping resampling procedure will estimate model test statistic  $p$  values and parameter standard errors (Arbuckle, 2006). Models will be considered to fit the data if the chi-square is not significant, Comparative Fit Index (CFI) is  $>.97$ , and root mean square error of approximation (RMSEA) is  $<.10$  (Bollen & Long, 1993) using an iterative basis, with individual paths added or deleted on the basis of modification indices (Jöreskog & Sörbom, 1984). Once a basic latent growth model is determined, treatment group will be added as a predictor of slope and intercept. Then, cognitive variables (pre to post change scores) included in the model. Beta weights of the full model can be tested using a product of coefficients test to determine if mediation is significant (MacKinnon 2007a,b).

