The fMRI sub-study will provide refined tests of hypotheses related to cognitive control in a subsample. The Stroop effect is calculated as the difference in reaction time between incongruent and congruent trials. In fMRI data, it is defined as difference in neural activity between incongruent and congruent trials.

1. To evaluate relationships between pre-treatment behavioral and neural measures of cognitive control during the Stroop task and treatment outcome, we will assess the Stroop effect and related neural activity and correlate these indices with treatment outcomes (e.g., longest duration of abstinence, % negative urines).
2. To assess changes in behavioral and neural measures of cognitive control, we will compare indices pre- to post-treatment (e.g., (Incongruent(pre) > congruent (pre)) > (Incongruent(post) > congruent (post))). We will also compare these indices between groups to identify treatment-specific changes.

The MID task allows examination of neural activity during anticipation and receipt of monetary rewards. Anticipation of reward is assessed by comparing neural activity during the reward anticipation phase, and contrasting conditions of \$0 and \$5 (Anticipation of \$5>\$0). Responses to receipt of monetary rewards are assessed by comparing neural activity during the outcome phase (Receipt of \$5>\$0).

1. To examine relationships between pre-treatment behavioral and neural measures of reward processing and treatment outcome, we will assess neural responses during anticipation and receipt of reward (\$5>\$0) and correlate these indices with treatment outcomes (longest duration of abstinence, % negative urines).
2. To evaluate the change in response to monetary rewards from pre- to post- treatment, we will compare indices from this task from pre- to post-treatment (e.g., anticipation of \$5 pre>post, and receipt of \$5 pre>post). We will also compare differences in these indices between groups to identify treatment-specific changes.

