- v. To protect participants who are eligible and agree to participate in the fMRI portion of the trial, all participants will be screened for appropriateness for fMRI using a screening form. All participants will be screened using a screening form for any metallic objects that they may be holding or have implanted in their bodies and all potential participants with metallic implants will be excluded. Individuals with occupational histories that might pose problems for MRI will be required to undergo additional safety procedures (e.g., individuals who have performed welding without eye protection will be required to obtain orbital x-rays prior to scanning). Similarly, other potential sources of metal (e.g., tattoos that contain magnetically sensitive metals), along with pregnancy will be investigated for compatibility with MRI. The Screener will be repeated prior to imaging to ensure that

participants are not bringing any metallic materials into close proximity of the magnet, where they might be pulled toward the magnet or heated by the magnet. As a routine part of neuroimaging, individuals are also required to walk through a metal detector prior to entering the room with the scanner.

Further, on the day of scanning, information about menstrual cycle (for women), tobacco use (for smokers, including pre- and post-scan carbon monoxide (CO) assessments), alcohol use (pre- and post-scan breathalyzer measures) and substance use (urine toxicology and self-report) will be obtained. Participants who are smokers will be given the opportunity to smoke about one hour prior to scanning in order to avoid acute intoxication or withdrawal effects from tobacco. Consistent with our prior fMRI studies, participants who are experiencing acute drug intoxication or withdrawal will not be scanned. Similarly to data from the main trial, all fMRI data will be coded by a unique code, and not names. Electronic data are stored on password-protected secured computers and paper information with PHI linked to the computerized data is kept secured in locked file cabinets in locked facilities

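### The imaging sub-study correlates pre-treatment brain measures with abstinence without adjusting for the baseline cocaine result, so a raw correlation may partly reflect recent use

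*Combined protocol and SAP*

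**What the plan says.** For the Stroop task, the fMRI part of Data Analysis states that "we will assess the Stroop effect and related neural activity and correlate these indices with treatment outcomes", giving longest duration of abstinence and percent negative urines as examples. The MID paragraph does the same for anticipation and receipt of reward. Neither names a covariate.

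Four other places bear on the point.

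- **Methods, Randomization.** The urn balances on the baseline cocaine result because "initial toxicology results are a strong predictor of outcomes". No analytic use of that result is stated there.
- **Data Analysis, opening paragraph.** The covariate rule is triggered by "Differences between groups that may be related to outcome".
- **Data Analysis, patient predictors of outcome.** The regressions list as independent variables "drug use severity (ASI-drug scores, baseline positive samples), scores on cognitive control tasks at baseline (computer task or impulsivity scores), and demographics", among others. The cognitive entries are computer-task or impulsivity scores; no fMRI index is listed.
- **Human Subjects, section 2.b.v.** On the day of scanning, "substance use (urine toxicology and self-report) will be obtained". Patients in acute intoxication or withdrawal are not scanned. A cocaine-positive urine is not named as a bar to scanning, and no analytic use of the scan-day data is described.

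The team's own earlier predictor analysis, under Preliminary studies, was run "Controlling for site, demographics (age, gender, education, race), and baseline drug use".

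**The concern.** A patient still using cocaine at intake may differ from an abstinent one in two ways: in later abstinence, which the plan states, and in neural response on the tasks, which is plausible but not quantified. If both hold, the brain measure and the outcome are correlated even when the brain measure carries no information beyond the intake urine result.

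Nothing elsewhere in the plan closes the gap. Urn balancing equalises the baseline result between arms; it does not remove confounding of a brain-outcome correlation within an arm or across arms. The covariate rule deals with imbalance between groups. The predictor regressions that carry baseline positive samples do not take in the imaging indices.

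What is at stake is interpretation. The plan hopes that cognitive measures will help direct reinforcement towards patients most likely to benefit. A costly brain measure helps with that only if it adds something to a routine urine test, and the specified correlation does not address this.

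**Working it through.** **The plan's own figure.** The sub-study has 30 patients per group (60 in all), said to suffice for correlations of 0.30 or more. No power is attached to that statement. Borrowing two-sided alpha 0.05 (the plan does not state sidedness) and 80% power from the primary aims, the Fisher z formula n = ((1.960 + 0.842)/atanh(0.30))² + 3 gives 85. Power at r = 0.30 is 36% with n = 30 and 65% with n = 60. The stated size is therefore not reproduced. That is a separate matter, and the present point does not depend on it. The plan does not say whether the correlations are run per group or pooled, so both sizes are used below.

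**Inputs that must be assumed.** The documents give no correlations for the baseline result. Take 0.3 to 0.5 for baseline result with outcome, and 0.2 to 0.4 for baseline result with neural index.

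**Induced correlation with no direct link.** r = r(baseline, outcome) × r(baseline, index).

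- Low: 0.3 × 0.2 = 0.06
- Middle: 0.4 × 0.3 = 0.12
- High: 0.5 × 0.4 = 0.20

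**Rejection rate of the unadjusted test.** Two-sided 5%, Fisher z, with shift = atanh(r) × √(n − 3) and both tails counted.

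| Induced r | n = 60: shift | n = 60: rejects | n = 30: shift | n = 30: rejects |
|---|---|---|---|---|
| 0.06 | 0.45 | 7% | 0.31 | 6% |
| 0.12 | 0.91 | 15% | 0.63 | 10% |
| 0.20 | 1.53 | 33% | 1.05 | 18% |

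**Check by simulation.** There were 20,000 samples per scenario, with a binary baseline result (30% in one category, an assumption) and no direct brain-outcome link. With components 0.2 (index) and 0.3 (outcome), the unadjusted test rejected in 7.5% at n = 60 and 6.2% at n = 30. With 0.3 (index) and 0.5 (outcome), induced r 0.15, it rejected in 21% and 12%. After partialling out the baseline result, rejection was about 5% in every scenario. Both components must be about 0.55 before confounding alone produces the plan's target of 0.30 (0.55 × 0.55 = 0.3025).

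**Cost of adjusting.** With one covariate partialled out, √(n − 3) becomes √(n − 4). If the partial correlation is 0.30, power goes from 64.7% to 63.9% at n = 60 and from 36.3% to 35.1% at n = 30, about one point.

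**If the raw correlation is 0.30 and the index is related to baseline use.** Partial r = (0.30 − ab)/√((1 − a²)(1 − b²)), where a and b are the two component correlations. Power is at n = 60.

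- 0.3 and 0.2: 0.24/√(0.91 × 0.96) = 0.26, power 50%
- 0.4 and 0.3: 0.18/√(0.84 × 0.91) = 0.21, power 35%
- 0.5 and 0.4: 0.10/√(0.75 × 0.84) = 0.13, power 16%

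The adjusted estimate can therefore be much smaller than the raw one. That is right if baseline use is a confounder and too severe if it lies on the pathway.

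**The case against.** The strongest reply is that the aim is associational. It sits among the secondary and exploratory aims and asks about relations between these measures and outcome; a raw correlation answers that. This stands. The raw correlation is a legitimate result, provided it is described as an association and not as prediction beyond baseline use.

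Second, the causal direction is open. The Innovation section argues that choices when drugs become available rely on cognitive control. If weak control leads to use at intake, the baseline result is on the pathway and adjusting for it removes genuine signal. This also stands. A reader might infer that only the adjusted estimate should count; the documents do not settle the direction, so neither estimate should be discarded.

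Third, the scan-day screen removes some acute drug effects. True, but it leaves recent, non-acute use. A reader might infer from the screen that the trial concedes recent use alters the scan. The text does not say so: it appears under protection against risks and names acute intoxication and withdrawal only.

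Fourth, a reader might infer that adjustment also buys power. If the index is unrelated to the baseline result, a true r of 0.30 becomes 0.30/√(1 − 0.3²) = 0.31 to 0.30/√(1 − 0.5²) = 0.35, and power at n = 60 rises from 65% to between 68% and 77%. But then there is no confounding to remove. The two benefits need incompatible conditions and cannot be claimed together.

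Finally, nothing in the plan forbids an adjusted analysis, and the variables are collected. That makes the gap easy to close, but does not make the adjustment pre-specified.

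**Conclusion.** The gap is real and specific to the imaging predictors: the plan includes baseline use in its non-imaging predictor models and leaves it out here. The consequence is a risk of unknown size, not a demonstrated bias. Over the assumed range, false rejection is modestly to substantially above 5%: about 7% to 33% pooled and 6% to 18% within one arm. These figures rest on the assumed component correlations and on there being no direct brain-outcome link.

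A reader might go further and conclude that any neural predictor found here is merely recent cocaine use. The documents do not support that, since they give no relation between the baseline result and the neural indices. Nor is there any bearing on the primary comparisons of the reinforcement arms, which do not use these analyses.

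**What to change.** In the fMRI part of Data Analysis, keep each raw correlation and pre-specify beside it a regression or partial correlation that includes the baseline cocaine result (positive or negative). When the arms are pooled, include treatment arm as well. State whether the analysis is pooled or within arm.

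Repeat the adjusted analysis with scan-day toxicology as a sensitivity check. It is closer in time to the scan, but the fMRI sub-study recruits after randomization, so it may be a post-assignment variable and fits less well as the main covariate.

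State the reporting rule: an index is said to predict outcome beyond baseline use only if the adjusted estimate supports it; the raw correlation is described as an association. Note that the adjusted estimate may be too small if weak cognitive control itself leads to use at intake, which is why both are shown.

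The cost is analysis wording and one or two degrees of freedom, about one point of power per covariate if the partial correlation is 0.30. No new data are needed.

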### **Design considerations:**

*Why these reinforcement parameters?* The parameters were chosen to be consistent with reinforcement schedules found previously efficacious and to equally reinforce abstinence in the two reinforcement conditions. The total number of draws possible is nearly identical ( $\pm 2$  draw) across conditions, and within each phase of reduced monitoring and reinforcement in Group C, overall possible reinforcement is similar to that in Group B. The continued escalating feature of reinforcement in Group C accommodates for the reduced frequency of testing and reinforcement, such that instead of earning 5 draws per negative sample twice a week, patients earn about 10 draws once per week. When further tapered to less than weekly testing, draws possible remain at about 20-25 draws every 2-3 weeks. Although this number of draws may appear to be a lot, it takes only about 2 min to select and open 25 slips, which translates to an expected average earning of about \$40 in prizes.

*Why this testing frequency?* A gradually decreasing frequency was selected to balance clinical, practical, and scientific considerations. In the first few weeks, some patients will not yet have achieved abstinence, and twice-weekly testing will detect all (or most all) drug use. Once abstinence is achieved, it does not appear necessary to monitor drug use as frequently, and random tests will ensure that use does not occur around known testing times. The schedule outlined should detect relapse as mean frequency of cocaine use is 10

days/month (Petry et al., 2012a), i.e., 2.5 days/week, which is likely to be detected at the next randomly selected testing day even during infrequent testing phases. Importantly, informing about testing and reinforcement days could be automated (computerized phone systems prompting samples) and continue long term (e.g., for  $\geq 1$  year) as a cost effective method to maintain abstinence if this study finds this intervention effective while it is in place. In contrast, requiring patients to come to a clinic twice weekly for 24 weeks (or longer), while also potentially efficacious, adds substantially to staffing and testing costs, as well as reinforcement costs.

*Will patients submit samples after leaving treatment, and will compensating sample submission confound results?* We have conducted studies in which patients were compensated for providing samples after leaving formal care (Petry et al., 2011a; prelim studies), and patients continued providing samples even when no longer engaged in clinical care. In an informal survey, 93% stated that patients would submit samples up to twice weekly for 6 months in exchange for unlimited cell service. Strict separation of treatment and research is maintained, with clinic staff encouraging engagement in research activities after treatment ends. If a patient were uncomfortable returning to the clinic after ending care, alternate locations for sample collection or evaluations can be arranged (see Human Subjects). Compensating patients for leaving samples or attending follow-ups increases those specific behaviors, but it has not impacted clinic attendance when research and clinical aspects are kept distinct; further, compensation for study procedures will be identical across groups.

*What if reinforcement is effective in the short- but not long-term?* We anticipate adaptive progressive VI reinforcement will be more likely than standard care (and even typical reinforcement procedures) to yield post-treatment benefits because it is likely to engage more patients in the reinforcement intervention longer and engender longer periods of abstinence, which is consistently linked with post-treatment outcomes (Higgins et al., 2000b; Petry et al., 2005a, 2007a, 2010b, 2011a, 2012ab). However, if long-term benefits do not occur, the adaptive reinforcement intervention could be maintained (even indefinitely in high-risk populations) to sustain benefits. Reinforcement once every 3 weeks on average is a low intensity intervention that may ultimately be a highly effective, relatively low cost maintenance approach applicable to a wide range of behaviors, including weight loss, medication adherence, exercise, and diabetes management (Petry et al., 2011b, 2012d, in press de). It is also less intensive than other forms of aftercare (1 hour weekly groups), requiring only 10 min of staff time.

*Are interventions generalizable?* Twice-weekly reinforcement interventions are already being implemented in clinics, as noted earlier. Although this adaptive progressive VI schedule is more complex, schedules of testing and reinforcing can be computerized and reminders set via cell phones, as we are doing (R21-DA029215, R01-HD075630). This system reduces frequency of monitoring as patients achieve more sustained periods of abstinence, similarly to methods of monitoring patient outcomes in other chronic diseases. For example, when blood pressure or A1cs remain in clinically accepted ranges, medical appointments are minimized, but when objective indices indicate difficulties in maintaining goals, intensities and frequencies of treatment increase. The National Business Group on Health (2013) reported that 85% of employers are now using reinforcers to promote health behaviors, and section 2705 of the Affordable Care Act allows employers to use up to 50% of total premiums for outcome-based incentives. Thus, insurers and society are recognizing the potential of reinforcement interventions to positively impact outcomes of diseases with behavioral components. Clinics, if appropriately reimbursed, could prompt, collect, test, and reinforce samples every 3 weeks from patients, even after they discontinue participation in traditional group therapy. This VI reinforcement intervention minimizes patients' and providers' time, thereby ultimately increasing potential for generalization.

**Data Quality Control:** Separation of clinical (treatment) and research components (structured evaluations) is critical. One RA will manage the reinforcement system, and another, blind to treatment conditions when possible, will conduct structured evaluations when possible. The project director will supervise implementation of treatments, assessing adherence and competence, and ensure equal and appropriate sample prompts

across conditions. Checksheets will be kept, listing data collected, draws earned and prizes won; sessions are audiotaped and reviewed for competence (Petry et al,2010a,2012bc).

**Data Analysis.** An important issue preceding analyses is to identify baseline differences between groups despite random assignment. Differences between groups that may be related to outcome (e.g., psychiatric diagnoses, dependence severity, clinic services received) will be used as covariates or fixed factors, as appropriate. Analysis will be conducted on an intent-to-treat basis, using all randomized patients, and both short-term (changes from baseline to month 6) and longer-term (throughout the 18-month follow-up) efficacy will be evaluated. The primary outcome is longest duration of cocaine abstinence, a continuous variable that can be transformed if needed. Groups will be compared using t-tests for normally distributed data, or ANCOVA if covariates are included. The design includes 3 treatment groups, allowing for analyses of two main effects.

Primary aim # 1 is to examine the efficacy of adaptive progressive VI reinforcement. We will compare those randomized to Group C vs Group A with respect to longest duration of abstinence during the 24-week intervention period and throughout the 18-month follow-up period.

Primary aim #2 is to assess if adaptive reinforcement improves duration of abstinence achieved relative to traditional reinforcement. We will compare those randomized to the two reinforcement conditions with respect to during treatment and long-term abstinence outcomes.

Secondary aims are to evaluate the impact of the interventions on other indices of stimulant and secondary drug use outcomes. Using the same contrasts above, we will compare groups with respect to: proportions of submitted and expected samples that test negative for stimulants and other drugs (alcohol, opioids, THC), and subjective reports of use (SUC % abstinent days). The first rely on objective indicators and such data will be available from all randomized patients. Subjective reports will supplement objective indices, and patients can be considered using if either index is positive. In terms of proportional data, missing samples will be considered missing (not impacting the denominator) in one analysis, and positive in another to consider the range of possibilities with respect to drug use outcomes. Because Group B has more expected samples (48) than the other groups ( $\geq 18$ ), proportional data for expected samples will rely upon the cell phone prompted samples ( $\geq 18$ ), designed to be similar across conditions, to conservatively test group differences.

**Power analyses for primary aims.** Our studies reinforcing abstinence generally find Cohen's  $d$  effect sizes of 0.6 to  $> 1.0$  for during treatment drug use outcomes (Petry et al, 2000, 2002,2004,2005abc,2006a, 2007a,2010b,2011a,2012abc). In terms of post-treatment effects, our ongoing study is finding an effect size of 0.46 for a 12-week reinforcement intervention in enhancing post-treatment abstinence relative to standard care. Although we expect a larger effect size when 24 weeks of reinforcement is provided, and especially if more patients engage in the adaptive progressive VI reinforcement intervention for greater durations, we will conservatively power this study to detect a similar effect size of 0.46 between the VI reinforcement intervention and standard care for long-term outcomes. Using a Type I error rate of  $\alpha=.05$ , a Type II error rate of  $\beta=.20$ , and power=0.80 (Cohen, 1988), 60 patients/ group are needed to detect  $d=0.46$  between the standard care and reinforcement interventions (Aim 1). For Aim 2, the study is powered to detect a lower, but still clinically meaningful, effect size of 0.35 between the two active reinforcement conditions, similar to effect sizes found between reinforcement conditions in other studies (Petry et al., 2004, 2006a). Using the same power analyses outlined above, 110 patients/group are needed to detect  $d \geq .35$  between the traditional and adaptive reinforcement conditions with respect to during treatment and long-term outcomes. Thus, we will recruit 280 patients (60 in standard care and 110 each for the reinforcement interventions).

**Secondary aims** are to evaluate if reinforcement improves other indices of drug use, psychosocial functioning (ASI, BSI scores), quality of life, and HIV risk behaviors, as found in other studies (Ghitza et al., 2008; Hanson et al, 2008; Petry et al., 2007b,in press b). These are continuous measures, with missing data likely. If no systematic differences in missing data are noted (the case in our prior studies), hierarchical linear models (HLM; Gibbons et al., 1993) using MIXREG (Hedeker, 1993) will analyze differences between groups over time. These analyses have advantages over repeated measures ANOVA as they estimate missing data via model parameter

estimates and use real time, rather than scheduled time, of assessments. Two contrasts will be explored. One will evaluate Aim 1, assigning a contrast weight of +1 to patients in VI reinforcement and -1 to standard care. For aim 2, we will assign contrast weights of +1 to those receiving adaptive reinforcement and -1 to traditional reinforcement. Analyses will be conducted for both short- (BL to M6, with up to 4 data points/ patient: BL,M1,M3,M6) and long-term effects (BL through M18, with up to 8 data points/patient: BL,M1,3,6,9,12, 15,18). The model will include factors for group (using contrasts above), time, and the interaction of group by time. These analyses will ascertain whether the interventions impact areas of functioning beyond drug use.

Changes in other drug use over time can also be examined using urinalysis data. Means of  $\geq 18$  samples will be scheduled for collection over 24 weeks, and  $\geq 22$  samples through the M18 follow-up. Samples will be coded as positive for any illicit drug or negative for all substances. HLM using MIXOR (Hedeker, 1996), an HLM program for dichotomous measures, will examine group changes over time, using contrasts above.

Moderators of effects will be explored. To date, we have investigated gender as a moderator of effects but never observed gender effects on drug use outcomes in reinforcement studies (e.g., Petry et al., 2005ac, 2006a,2010b,2011a,2012a), perhaps in part because we provide highly desired prizes for both men and women (Petry, 2012). Nonetheless, effects of gender will be explored, as will interactions between gender, treatment condition, and other characteristics that may impact outcomes. Although we do not anticipate gender differences in main outcomes, we expect to find gender-specific HIV risk behaviors (Barry et al., 2008; Rash & Petry, 2009). We have also found that women show greater heritability of impulsive responding on cognitive tasks than men (Petry et al., 2002) and women with addictive disorders and ASPD are particularly impulsive (Andrade et al., under review).

To determine if patient factors predict outcome, multiple regression analyses will be used to find predictors of continuous measures (e.g., longest duration of abstinence, percent negative samples), and logistic regressions for dichotomous dependent variables (e.g., presence or absence of stimulant use at follow-up). Cox regression analyses may also be used to determine what factors predict time to event outcomes, such as time to first positive sample after study initiation. Independent variables will include treatment condition, site, days attended groups at the clinic, drug use severity (ASI-drug scores, baseline positive samples), scores on cognitive control tasks at baseline (computer task or impulsivity scores), and demographics, including gender and race. Analyses will be conducted for the entire sample and with interactions of predictors with condition to assess if certain characteristics are more predictive of outcomes in the different treatment conditions.

Behavioral changes that result from treatment may also be a function of improving cognitive control, and reinforcement interventions may lead to reductions in drug use by enhancing cognitive functioning. If effects of reinforcement on drug use outcomes are significant, cognitive control as assessed via computer and impulsivity tasks will be evaluated as a potential mediator of effects. A latent growth model using structural equation modeling can be built. Models will be built sequentially, starting with a basic latent growth model comprising drug use days over time, modeled as slope and intercept. Important cognitive performance indices can be tested as mediators in turn. A bootstrapping resampling procedure will estimate model test statistic  $p$  values and parameter standard errors (Arbuckle, 2006). Models will be considered to fit the data if the chi-square is not significant, Comparative Fit Index (CFI) is  $>.97$ , and root mean square error of approximation (RMSEA) is  $<.10$  (Bollen & Long, 1993) using an iterative basis, with individual paths added or deleted on the basis of modification indices (Jöreskog & Sörbom, 1984). Once a basic latent growth model is determined, treatment group will be added as a predictor of slope and intercept. Then, cognitive variables (pre to post change scores) included in the model. Beta weights of the full model can be tested using a product of coefficients test to determine if mediation is significant (MacKinnon 2007a,b).

